AE/SAE assessment	X	X	X		8.3
Concomitant medications	X	X	X		6.4
Performance Score (Lansky or Karnofsky) performance status ^b	X				8.2.7
Subsequent anticancer therapy ^c	X	X	X	X	8.1.2
Survival status ^d	X	X	X	X	8.1.2
Hematology	X	X	X		Table 20
Clinical chemistry	X	X	X		Table 19
TSH ^e (if abnormal free T4 \pm free T3)	X	X	X		Table 19
Durvalumab PK sample (serum) ^f			X		8.5
Tremelimumab PK sample (serum) ^f			X		8.5
Durvalumab immunogenicity assessment ADA (serum) ^f			X		8.5

	Time since last dose of IP				For details, see Section
	Day (± 3)	Months (± 1 week)			
	30	2	3	4 months and every 2 months thereafter (± 2 weeks)	
Evaluation					
Tremelimumab immunogenicity assessment ADA (serum) ^f			X		8.5
Radiological efficacy assessments ^g	Efficacy assessments occur every 8 weeks (or every 16 weeks for patients who achieve an objective response [CR, PR] or stable disease and for whom the response is still evident at 12 months) ± 1 week relative to the date of first dose, until radiological progression plus an additional regularly scheduled follow-up scan or death (whichever comes first). Additional scans to be completed per standard practice post-progression				7.1

Note: Patients who permanently discontinue drug for reasons other than objective PD should continue to have objective response assessments performed every 8 weeks ± 1 week (when clinically indicated) thereafter until PD plus an additional follow-up assessment or death (whichever comes first). For patients who achieve an objective response (CR, PR) or stable disease and for whom the response is still evident at 12 months, subsequent tumor assessments are to occur every 16 weeks. If a patient is discontinued for PD, then the patient should have 1 additional follow-up assessment performed preferably at the next (and no later than the next) scheduled imaging visit, and no less than 4 weeks after the prior assessment of PD.

^a For females of childbearing potential only. A urine or serum pregnancy test is acceptable.

^b Karnofsky scale to be used for patients ≥ 16 years of age; Lansky scale to be used for patients ≥ 1 and < 16 years of age.

^c Details of any treatment **for the malignancy under study** (including surgery) post the last dose of IP must be recorded in the CRF. At minimum, collect the start date and description of the subsequent anticancer therapy.

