7.1.1 Procedures for discontinuation of study treatment

Discontinuation of study treatment, for any reason, does not impact the patient's participation in the study. A patient or his/her parent(s)/legally authorized representative(s) who decides to discontinue IP will always be asked about the reason(s) for discontinuation and the presence of any AE. The patient should continue attending subsequent study visits, and data collection should continue according to the study protocol. If the patient or his/her parent(s)/legally authorized representative(s) does not agree to continue in-person study visits, a modified follow-up must be arranged to ensure the collection of endpoints and safety information. This follow-up could be a telephone contact with the patient or his/her parent(s)/legally authorized representative(s), a contact with a relative or treating physician, or information from medical records. The approach taken should be recorded in the medical records. A patient or his/her parent(s)/legally authorized representative(s) that agrees to modified follow-up is not considered to have withdrawn consent or to have withdrawn from the study.

Patients who are permanently discontinued from further receipt of IP, regardless of the reason, will be identified as having permanently discontinued treatment. Patients who are permanently discontinued will enter follow-up (see the SoAs).

Patients who permanently discontinue drug for reasons other than objective PD should continue to have OR assessments performed every 8 weeks \pm 1 week relative to the date of the first dose until PD plus an additional follow-up assessment or death (whichever comes first) as defined the SoAs.

If a patient is discontinued for PD, then the patient should have 1 additional follow-up assessment performed preferably at the next (and no later than the next) scheduled imaging visit, and no less than 4 weeks after the prior assessment of PD.

All patients will be followed for survival until the end of the study.

Patients or his/her parents/legally authorized representatives who decline to return to the site for evaluations should be contacted by telephone as indicated in the SoAs as an alternative.

Patients who have permanently discontinued from further receipt of IP will need to be discontinued from the IRT/RTSM (Note that IRT/RTSM will only be used for the dose-expansion phase. Dose-finding phase will be manually supplied/managed).

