8.1 Efficacy assessments

Efficacy assessments of ORR, duration of response (DoR), DCR, and PFS will be derived (by AstraZeneca) using the response criteria defined below. Overall survival will also be assessed for each individual patient.

Tumor assessments will be done in accordance with the type of tumor: NB ([Appendix F](#)), other solid tumors ([Appendix E](#)).

Radiological assessments will be made following routine clinical practice procedures during screening and then every 8 weeks (relative to the date of Cycle 1 Day 1), until radiological progression. For patients who achieve an objective response (CR, PR) or stable disease and for whom the response is still evident at 12 months, subsequent tumor assessments are to occur every 16 weeks. Unscheduled assessments can be performed at any time during the study, as clinically indicated, based on signs and symptoms. Disease progression requires confirmation, the confirmatory scan should occur preferably at the next scheduled visit and no earlier than 4 weeks after the initial assessment of PD in the absence of clinically significant deterioration. Treatment will continue between the initial assessment of progression and confirmation for progression.

Tumor assessments will be made during screening/baseline and at regular (follow-up) intervals during study treatment. Pelvic imaging is recommended only when primary or metastatic disease in the pelvic region is likely. Any other areas of disease involvement should be additionally imaged based on the signs and symptoms of individual patients. It is important to follow the tumor assessment schedule as closely as possible (refer to the SoAs). If an unscheduled assessment is performed (eg, to investigate clinical signs/symptoms of progression) and the patient has not progressed, every attempt should be made to perform the subsequent assessments at the next scheduled visit. Treatment continues until clinical progression/deterioration or confirmed radiological progression, and scanning/tumor assessments continue throughout treatment until radiological progression plus an additional follow-up scan (if clinically feasible).

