3 PRIMARY AND SECONDARY VARIABLES

3.1 Derivation of visit tumor responses

The analysis of the primary endpoint, ORR, and the analyses of the secondary endpoints, PFS, DoR, and DCR, will be based on the site Investigator assessments using the following criteria

Table 5 Criteria for Investigator assessments

Type of cancer	Criteria
Solid Tumors	
SARCOMA and STO	RECIST 1.1 (see CSP Appendix E)

All RECIST 1.1, whether scheduled or unscheduled, will be included in the calculations. This is also regardless of whether a patient discontinues study treatment or receives another anticancer therapy.

Baseline will be assessed within the 21 days prior to first dose of study treatment and ideally as close as possible to the start of study treatment. Assessments are performed every 8 weeks (relative to the date of first dose of study treatment) in the first instance. For patients who achieve an objective response or stable disease, and for whom the response is still evident at 12 months, subsequent tumor assessments are to occur every 16 weeks \pm 1 week until disease progression.

If an unscheduled assessment is performed, and the patient has not progressed, every attempt should be made to perform the subsequent assessments at their scheduled visits. This schedule is to be followed in order to minimise any unintentional bias caused by some patients being assessed at a different frequency than other patients.

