3.2.2 Progression-free survival (PFS)

Progression free survival (per RECIST 1.1, as assessed by the site Investigator) will be defined as the time from the date of first dose of study treatment until the date of objective disease progression or death (by any cause in the absence of progression) regardless of

whether the patient withdraws from study therapy or receives another anti-cancer therapy prior to progression (i.e. date of PFS event or censoring – date of first dose + 1). Patients who have not progressed or died at the time of analysis will be censored at the time of the latest date of assessment from their last evaluable RECIST 1.1 assessment. However, if the patient progresses or dies after 2 or more missed visits, the patient will be censored at the time of the latest evaluable (RECIST 1.1) assessment prior to the 2 missed visits (Note: NE visit is not considered a missed visit).

Given the scheduled visit assessment scheme (i.e. eight-weekly (+/-1 week) for the first 12 months with the option of moving to every 16 weeks \pm 1 week thereafter (for those with a sustained objective response), until clinical progression/deterioration) the definition of 2 missed visits will change over time on a per patient basis.

If the previous (RECIST 1.1) assessment is between study day 49 (i.e. week 7) and less than the last assessment on an 8-weekly schedule then two missed visits will equate to 18 weeks since the previous RECIST 1.1 assessment, allowing for early and late visits (i.e. 2 x 8 weeks + 1 week for an early assessment + 1 week for a late assessment = 18 weeks). If the two missed visits occur over the period when the scheduled frequency of RECIST 1.1 assessments changes from eight-weekly to sixteen-weekly this will equate to 26 weeks (i.e. take the average of 8 and 16 weeks which gives 12 weeks and then apply same rationale, hence 2 x 12 weeks + 1 week for an early assessment + 1 week for a late assessment = 26 weeks). Once the scheduling changes to sixteen-weekly assessments, two missing visits will equate to 34 weeks (i.e. 2 x 16 weeks + 1 week for an early assessment + 1 week for a late assessment = 34 weeks).

If a patient has no evaluable visits or does not have baseline data, they will be censored at day 1 unless they die within 2 visits of baseline (16 weeks plus 1 week allowing for a late assessment within the visit window) then they will be treated as an event with date of death as the event date.

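### The Table 3 note makes off-treatment response scans conditional on clinical indication, contradicting the fixed calendar in the Table 3 row, Section 7.1.1 and SAP 3.1

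*Protocol*

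**What the plan says.** Four places in the protocol bear on scans after drug is stopped.

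- **Table 3, radiology row (Section 1.1):** "Efficacy assessments occur every 8 weeks (or every 16 weeks for patients who achieve an objective response" or stable disease still evident at 12 months), within 1 week either way, "relative to the date of first dose, until radiological progression plus an additional regularly scheduled follow-up scan or death (whichever comes first"). There is no clinical condition.
- **Table 3, note (Section 1.1):** this addresses patients who permanently stop drug for reasons other than objective PD. It keeps the 8-weekly interval and the later 16-week provision, but qualifies the 8-weekly scans with "when clinically indicated) thereafter until PD plus an additional follow-up assessment or death (whichever comes first"). It does not mention the first dose.
- **Section 7.1.1:** for the same patients, every 8 weeks "relative to the date of the first dose until PD plus an additional follow-up assessment or death (whichever comes first) as defined the SoAs". There is no clinical condition and no 16-week provision.
- **Section 8.1 (general schedule):** "during screening and then every 8 weeks (relative to the date of Cycle 1 Day 1), until radiological progression", again without condition, with the 16-week provision following.

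The SAP relies on the calendar. SAP 3.1 counts every RECIST 1.1 assessment whether or not the patient is still on treatment, and says of the schedule: "This schedule is to be followed in order to minimise any unintentional bias" from patients being assessed at different frequencies. SAP 3.2.2 adds that "if the patient progresses or dies after 2 or more missed visits, the patient will be censored" at the latest evaluable assessment before the gap.

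**The concern.** The note and the row sit in one table, cover overlapping patients and give different rules. Section 7.1.1 does not settle the matter, because it refers back to the schedule tables. No text says which rule governs.

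A site that follows the note may scan a patient who has stopped drug only when symptoms call for it. Two sets of endpoints are then exposed. The primary ORR counts only responses confirmed on a scan at least 4 weeks later. PFS, and through it DoR, APF12 and APF18, depends on when progression is detected and on how long the patient has gone without a scan. The patients affected are those who stop early without progression, so the unequal scan frequency would be tied to their course on study.

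**Working it through.** **1. The texts side by side**

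| Place | Condition on scheduled scans | First-dose anchor | 16-week provision |
|---|---|---|---|
| Table 3 row | none | yes | yes |
| Table 3 note | clinical indication | no | yes |
| Section 7.1.1 | none | yes | no |
| Section 8.1 | none | yes (Cycle 1 Day 1) | yes |
| SAP 3.1 | none | yes | yes |

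The note is the only text with the condition and the only one without the anchor. Section 7.1.1 is the only one without the 16-week provision.

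**2. Effect on the primary ORR**

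Take a PR at the week 8 scan, after which drug is stopped for toxicity. On the fixed calendar the next scan is at week 16. With both 1-week windows used against it, the gap is 15 − 9 = 6 weeks, which still exceeds the 4 weeks needed for confirmation. Under the note, a clinically well patient may have no scan then. SAP Table 3 requires measurable disease at baseline, one follow-up scan of all required target lesions and at least 3 cycles of follow-up. A patient who meets these stays in the denominator as a non-responder.

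**3. Effect on PFS and the endpoints derived from it**

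SAP 3.2.2 sets the two-missed-visit limits:

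- 8-weekly: 2 × 8 + 1 + 1 = 18 weeks (126 days)
- across the switch: 2 × 12 + 1 + 1 = 26 weeks
- 16-weekly: 2 × 16 + 1 + 1 = 34 weeks

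Suppose the last scan is at week 16 and progression would have been visible at week 24.

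- If the next scan, done on symptoms, is at week 32, the gap is 16 weeks. This is under 18, so progression counts but is dated 8 weeks late.
- If it is at week 40, the gap is 24 weeks. This is over 18, so the event is dropped and the patient is censored at week 16.

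A death after such a gap is censored in the same way. Late dating lengthens observed PFS, and dropping events tends to do so. DoR uses the PFS event or censoring date (SAP 3.2.4). APF12 and APF18 are read from the PFS curve (SAP 3.2.7).

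**4. The design, and how sensitive it is**

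Inputs from Section 9.2: null ORR 10%, alternative 30%, one-sided alpha 0.10, power at least 85%; stop if fewer than 2 of 11 respond; reject the null if 5 or more of 26 respond.

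- P(stop at Stage 1) = (1 − p)^11 + 11p(1 − p)^10. At p = 0.30 this is 0.0198 + 0.0932 = 0.113.
- P(reject) = Σ over x ≥ 2 of P(X₁ = x) · P(X₂ ≥ 5 − x), with X₁ ~ Bin(11, p) and X₂ ~ Bin(15, p). This is 0.0865 at p = 0.10 and 0.8516 at p = 0.30.

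A full search for the optimal design under these inputs returns the same boundaries (1/11, 4/26), so the plan's figure is reproduced.

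The documents give no share of responses that would lose confirmation. Treating that share s as an assumption, with true ORR 30% and confirmed ORR 0.30 × (1 − s):

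| s | Confirmed ORR | Power | Stop at Stage 1 |
|---|---|---|---|
| 0% | 30.0% | 85.2% | 11.3% |
| 5% | 28.5% | 81.9% | 13.4% |
| 10% | 27.0% | 78.0% | 15.9% |
| 20% | 24.0% | 68.4% | 21.9% |
| 30% | 21.0% | 56.4% | 29.4% |

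This shows how sensitive the rule is to lost confirmations. It does not estimate the loss.

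**The case against.** The best defence is that the intended design is plain. The note itself says assessments should continue 8-weekly. The row, Section 7.1.1 and Section 8.1 carry no condition, and the synopsis paragraph on follow-up after discontinuation restates Table 3 without it. Most sites would probably keep scanning. That stands, and it is why the consequences are possible and not established.

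Confirmation also has some separate protection. The imaging footnotes to Tables 1 and 2 require confirmatory scans, and the SAP's evaluable-set definition allows time for one 4 weeks after the first assessment. This is partial: those footnotes belong to the on-treatment tables, and the Table 3 imaging footnote does not repeat the requirement. The SAP's sensitivity analysis on unconfirmed CR/PR would reveal lost confirmations. It would not change the primary confirmed ORR or repair PFS or DoR.

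The qualifier might be read as referring to extra scans. The protocol describes those separately, as unscheduled assessments on clinical indication, whereas in the note the condition attaches to the scheduled ones. The word 'thereafter' alone may only mean 'from then on'. The missing anchor is the difference that matters.

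A reader might infer a size from the roughly 15% of adults who stopped the combination for an AE (Section 2.3.2.3): 0.15 × 26 = 3.9 SARCOMA patients. That counts patients who might come under the note, assuming the adult rate and no PD at discontinuation. It does not count confirmations at risk. Responders among them would number about 3.9 × 0.30 = 1.2 at a 30% ORR, or 3.9 × 0.10 = 0.4 at 10%. Of these, only patients who stop between the first CR/PR scan and the confirming scan, and are then not scanned, would be lost.

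**Conclusion.** Wrong as written. The Table 3 note conflicts with the row of its own table, with Sections 7.1.1 and 8.1, and with the fixed schedule that SAP 3.1 relies on. A site that follows the note can leave a response unconfirmed in the primary ORR, and can cause progression to be dated late or censored.

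The documents do not support the stronger reading that responses will be lost or that the SARCOMA decision will change. That depends on how sites read the note and on how many responders stop drug in the relevant window, and neither is stated. One lost confirmation is 1/26 = 3.8 percentage points of ORR. Against thresholds of 2 of 11 and 5 of 26 it would matter only in a borderline cohort. The 18-week limit should not be carried over to the whole APF18 period, since it becomes 26 and then 34 weeks for patients who move to 16-weekly scans. The design calculation itself is sound.

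**What to change.** Reconcile the passages so that one unconditional off-treatment assessment calendar applies until PD.

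1. In the Table 3 note, replace the parenthesis on clinical indication and the word 'thereafter' with the anchor to the date of first dose. Deleting the words alone would leave the note without an anchor.
2. In Section 7.1.1, add the 16-week provision already in the Table 3 row and note. Without it, that section would still differ from Table 3.
3. Leave scans on clinical indication as additional, unscheduled assessments, as Section 8.1 already describes them.

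The cost is a wording amendment. The row and Section 7.1.1 already require the scans, so no procedure is added. Sample size, alpha and planned power (85.2%) are unchanged.

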1.2 Synopsis

International Co-ordinating Investigator:

PPD

Address: PPD

, [name]

Protocol Title: Phase I/II, Open-Label, Multicenter Study to Evaluate the Safety, Tolerability, and Preliminary Efficacy of Durvalumab Monotherapy or Durvalumab in Combination with Tremelimumab in Pediatric Patients with Advanced Solid Tumors and Hematological Malignancies.

Rationale: This is a first time in pediatrics study primarily designed to evaluate the safety and tolerability of durvalumab and durvalumab in combination with tremelimumab at increasing doses in pediatric patients with advanced solid malignancies who have progressed or are refractory to standard therapies and for whom no standard of care treatments exist. Although treatment efficacy is not a primary objective of this study given its early phase nature, the patients screened for this study have no standard treatment options and this study offers the potential of some benefit.

The study will also characterize the PK of durvalumab and durvalumab in combination with tremelimumab in children and adolescents and explore potential biological activity and immunogenicity by assessing pharmacodynamics, anti-drug antibody (ADA) levels, and anti-tumor activity. The results from this trial will form the basis for decisions for potential future pediatric studies.

Objectives and Endpoints

Primary Objective (Dose-finding phase):	Endpoint/Variable:
To determine the adult equivalent exposure/MTD/recommended Phase II pediatric dose of durvalumab in combination with tremelimumab and durvalumab as monotherapy following combination therapy.	Based on PK parameters (including C_{max} , C_{min} , AUC, and others), identify the adult equivalent exposure/MTD of durvalumab in combination with tremelimumab and durvalumab as monotherapy following combination therapy, among children and young adults from birth to <18 years of age with advanced solid tumors using a q4w dosing schedule. Time of RP2D assessment will be at the end of the dose-finding phase, when sufficient numbers of evaluable samples have been accrued.

Objectives and Endpoints

To determine the safety profile of durvalumab in combination with tremelimumab and durvalumab as monotherapy following combination therapy	Identify the safety and tolerability of durvalumab in combination with tremelimumab and durvalumab as monotherapy following combination therapy at the adult equivalent exposure/MTD among children and young adults from birth to <18 years of age with advanced solid tumors using a q4w dosing schedule. Endpoints include AEs, vital signs, physical examinations, ECGs, and laboratory evaluations.
Primary Objective (Dose-expansion phase):	Endpoint/Variable:
To determine the preliminary antitumor activity of durvalumab in combination with tremelimumab and durvalumab as monotherapy following combination therapy, at the recommended dose, using cohort-specific response criteria (eg, RECIST 1.1).	Objective response rate as determined by the Investigator assessed RECIST 1.1 or alternative pre-specified tumor-specific response rates for different scoring systems. Assessment of antitumor activity will be specific to tumor cohort, eg, Investigator assessed RECIST 1.1. Additional efficacy endpoints that will be collected include DoR, BoR, DCR, PFS, APF12, and APF18 based on RECIST 1.1 assessed by the Investigator, and OS, OS12, and OS24 as appropriate to each individual cohort.
Secondary Objective (Dose-finding and Dose-expansion phases):	Endpoint/Variable:
To describe the PK of durvalumab and tremelimumab in combination and durvalumab as monotherapy following combination therapy, in children and young adults with solid tumors, or hematological malignancies.	Individual durvalumab and tremelimumab concentrations in serum, and PK parameters including C_{max} , C_{min} , AUC, and other parameters where appropriate.
To determine the immunogenicity of durvalumab and tremelimumab in combination and durvalumab as monotherapy following combination therapy, in children and young adults with solid tumors.	CCI [REDACTED]

Objectives and Endpoints

To determine the immunogenicity of durvalumab in combination with tremelimumab and durvalumab as monotherapy following combination therapy, in children and young adults with hematological malignancies.	CCI [REDACTED]
To measure effects on immune checkpoint inhibition in response to routine immunizations (dose-expansion phase only).	Individual antibody titer measurements CCI [REDACTED]
To evaluate immune activation and counts of NK-, B- and T-cells.	CCI [REDACTED]
Safety objective:	Endpoint/variable:
To determine the safety profile and tolerability of patients from dose-expansion cohort(s) treated with durvalumab in combination with tremelimumab with a q4w dosing schedule.	Adverse events, vital signs, physical examinations, ECGs, and laboratory evaluations.
Exploratory objective:	Endpoint/variable:
To collect biomarker and immune response data in patients treated with durvalumab in combination with tremelimumab and durvalumab as monotherapy following combination therapy.	The endpoints related to candidate predictive and/or prognostic biomarkers will focus on CCI [REDACTED], acknowledging that pediatric patients with advanced cancer have limitations on CCI [REDACTED] that can be harvested for correlative studies. If technically feasible the current translational plan will include assessment of: CCI [REDACTED]

Objectives and Endpoints

In addition, an exploratory assessment related to biomarkers will be performed based on the availability of CCI [REDACTED] to examine the relationship between a patient's health CCI [REDACTED] prior to treatment as well as any modulations which may occur during and/or following treatment relative to clinical outcome, as applicable. If samples are available, assays may include:

CCI [REDACTED]

To compare RECIST 1.1 with irRECIST as assessment methodologies for clinical benefit of durvalumab and durvalumab in combination with tremelimumab.

Progression-free survival (and ORR) according to RECIST 1.1 and irRECIST (irRECIST will only be used as an exploratory endpoint).

ADA Anti-drug antibody; AE Adverse event; APF12 / APF18 Proportion of patients alive and progression-free at 12 / 18 months from first dose of IP; AUC Area under the plasma drug concentration-time curve; BoR Best objective response; CD Cluster of differentiation; C_{max} Maximum serum concentration; C_{min} Minimum serum concentration; DCR Disease control rate; DoR Duration of response; ECG Electrocardiogram; CCI [REDACTED]; IFN Interferon; irRECIST immune-related Response Evaluation Criteria in Solid Tumors; MTD Maximum tolerated dose; NK Natural killer; ORR Objective response rate; OS Overall survival; CCI [REDACTED] PK Pharmacokinetics; q4w Every 4 weeks; RECIST Response Evaluation Criteria in Solid Tumors; RP2D Recommended Phase II dose; CCI [REDACTED].

Overall design:

Open-label, non-randomized, international, multicenter study investigating durvalumab in combination with tremelimumab (q4w for 4 cycles only) followed by durvalumab monotherapy (q4w) in pediatric patients from birth to <18 years of age with relapsed or refractory malignant solid tumors. Durvalumab in combination with tremelimumab will be examined in all solid malignant tumors (except primary central nervous system tumors).

The study will be conducted in 2 sequential phases: a dose-finding phase, followed by a dose-expansion phase.

Each treatment cycle is 28 days.

Phase I: Dose-finding phase

The dose-finding phase of the study will be conducted using a modified 3 + 3 design to determine whether durvalumab and tremelimumab can be administered safely in pediatric patients and if adult exposures can be achieved. Pediatric patients with relapsed or refractory malignant solid tumors (osteosarcoma and Ewing sarcoma [SARC-1], rhabdomyosarcoma, non-rhabdomyosarcoma, and other sarcomas [SARC-2], neuroblastoma [NB]), other solid tumors (STO), will be enrolled in 2 arms:

- Arm A: patients weighing ≥ 35 kg
- Arm B: patients weighing < 35 kg.

[figure not shown]
Patients will be treated in Cycle 1 with durvalumab monotherapy, Cycles 2 to 5 with durvalumab combined with tremelimumab, and from Cycle 6 with durvalumab alone until progression of disease (PD).

Based on the available clinical and PK data and simulations, the administration of an adult weight-adjusted dose in children with a body weight of ≥ 35 kg is anticipated to result in PK and target engagement profiles similar to adults. However, patients with a body weight less than 35 kg, may have exposures lower than those in adults, and thus may require higher doses to achieve exposures similar to adults. Consequently dose-finding will be conducted in 2 body weight-based arms (ie patients, ≥ 35 kg and < 35 kg) in parallel. Based on emerging data during the conduct of the study, cohorts may also be backfilled to provide further assessment of safety and PK in specific age groups and to ensure a broad representation of ages/weights at a given dose level (DL).

Three DLs may be explored in each of the arms as outlined in the figure below. Dose level 1 will be 100% of the recommended adult dose of both durvalumab and tremelimumab administered as weight-adjusted doses. The doses and schedules are as follows:

1. Cycle 1 (durvalumab monotherapy): durvalumab 20 mg/kg
2. Cycles 2 to 5 (durvalumab in combination with tremelimumab): durvalumab 20 mg/kg and tremelimumab 1 mg/kg (4 cycles administered every 28 days)
3. From Cycle 6 onwards, treatment will continue until a discontinuation criterion is met, with durvalumab monotherapy administered at 20 mg/kg every 28 days.

This figure shows the maximum doses for durvalumab at DLs 2 and 3 (40 mg/kg) and tremelimumab at DL 3 (2 mg/kg). Lower doses may be tested, depending on the obtained PK modeling data.

DL Dose level; NB Neuroblastoma; SARC-1 Osteosarcoma and Ewing sarcoma; SARC-2 Rhabdomyosarcoma, non-rhabdomyosarcoma, and other sarcomas; STO Solid tumor other.

A Data Review Committee (DRC) will be established prior to the initiation of the study to review all the data, including with a primary emphasis on safety and PK, to make decisions on dose escalations and determination of a recommended Phase II dose (RP2D) to be further explored in the dose-expansion phase.

Dose escalation decisions will aim to identify the RP2D for durvalumab and tremelimumab in combination. Dose escalation decisions and determination of RP2D will mainly consider safety assessments from at least 3 patients followed up for 4 cycles, to include a single cycle of durvalumab and 3 cycles of the combination of durvalumab and tremelimumab (for a total of 120 days). This includes assessment of pre-defined dose-limiting toxicities (DLTs) in the first 2 cycles.

A de-escalation step may occur for durvalumab or tremelimumab, with reduced doses of 15 mg/kg and 0.75 mg/kg, respectively, if DL 1 is considered not tolerated. Furthermore, if exposure of durvalumab or/and tremelimumab proves inadequate, intermediate DLs may also be tested.

In addition, 3 patients older than 2 years of age must be treated with durvalumab in combination with tremelimumab and clear the DLT period before children less than 2 years old may be enrolled in the dose-finding phase.

Phase II: Dose-expansion phase

The dose-expansion phase will be conducted using a Simon 2-stage optimal design with an additional provision to include 1 mixed disease cohort (other malignant solid tumors).

Once the RP2D has been established, patients will be recruited to each of the following cohorts:

1. SARCOMA (bone sarcomas: osteosarcoma, Ewing sarcoma; soft-tissue sarcomas [$\geq 40\%$ of enrollment]: rhabdomyosarcoma, non-rhabdomyosarcoma, and other sarcomas)
2. STO (other solid tumors).

For the SARCOMA cohort, the initial stage will allow 11 evaluable patients, to be dosed in this disease-specific cohort. If 2 or more responses in either of these cohorts are observed, additional patients will be accrued, as part of the second stage, into the corresponding expansion cohort; 15 patients will be accrued into the SARCOMA expansion cohort for a total of 26 evaluable patients. If there has been ≤ 1 objective response in the SARCOMA cohort (11 patients), at the time that evaluable patients dosed in the initial stage have been followed/assessed for at least 3 cycles, the cohort will be discontinued for lack of benefit.

For the STO cohort, 10 evaluable patients will be enrolled into this mixed-disease cohort; Simon rules are not applicable for this cohort.

Study period:

Date of first patient enrolled: Q1 2019.

Estimated date of last patient completed: Q1 2023.

Number of patients:

Dose-finding phase: The final sample size in the dose-finding phase will depend on the number of DLTs and on the number of DLs to be explored. In addition, any patients not evaluable will be replaced in order to have the required number of patients evaluable at each DL. A minimum of 12 patients is anticipated to be dosed, to enable exploration of one DL in both patients weighing 35 kg and greater, and patients weighing under 35 kg. If all 3 DLs are used at both weight-based arms, then 36 evaluable patients would be necessary to complete the dose-finding phase. If approximately 20% of patients need to be replaced due to non-evaluability, then a maximum of 45 patients will be enrolled on the dose-finding cohorts.

Dose-expansion phase:

- Following a Simon 2-stage optimal design, a total of 26 evaluable patients (11 evaluable patients in the initial stage and an additional 15 patients in the second stage), are expected to be enrolled in the SARCOMA cohort.
- The STO cohort is planned to recruit 10 evaluable patients.

With the above considerations, the sample size for evaluable patients in the dose-expansion phase is expected to range from 38 to 66. Assuming that about 20% of patients may not be evaluable for objective response rate (ORR), the total number of patients dosed in the dose-expansion phase may range from approximately 46 to 80.

Screen failures are patients who do not fulfill the eligibility criteria for the study, and therefore must not be dosed. Patients may be rescreened a single time.

Treatments and treatment duration:

Durvalumab + tremelimumab combination therapy (dose-finding phase):

- Durvalumab monotherapy, administered as a single cycle, will be given via intravenous (IV) infusion at Cycle 1. Patients will receive durvalumab in combination with tremelimumab via IV infusion q4w, starting on Cycle 2, for up to a maximum of 4 doses/cycles. Four weeks after the last infusion of the combination, treatment continues with durvalumab monotherapy q4w until clinical or confirmed PD, or other discontinuation criteria is met, whichever comes first.

Durvalumab + tremelimumab combination therapy (dose-expansion phase):

- Durvalumab in combination with tremelimumab via IV infusion q4w will be given for up to a maximum of 4 doses/cycles. Four weeks after the last infusion of the combination, treatment continues with durvalumab monotherapy q4w until clinical or confirmed PD, or other discontinuation criteria is met, whichever comes first.

Duration of treatment

Unless specific treatment discontinuation criteria are met, patients will continue therapy until clinical progression/deterioration or confirmed radiological progression, and scanning/tumor assessments continue throughout treatment until radiological progression plus an additional follow-up scan (if clinically feasible).

Progression during treatment

All patients will receive 4 cycles of durvalumab in combination with tremelimumab (Cycles 2 to 5 in the dose-finding phase and Cycles 1 to 4 in the dose-expansion phase). Treatment with durvalumab alone will be continued q4w until clinical progression or confirmed radiological progression, unless there is unacceptable toxicity, withdrawal of consent, or another discontinuation criterion is met.

If a patient progresses while receiving durvalumab monotherapy after receiving an initial 4 cycles of the combination of durvalumab and tremelimumab, such patients may restart treatment with the combination treatment for 4 additional cycles.

Follow-up of patients post discontinuation of study drug

Patients who have discontinued treatment due to toxicity or symptomatic deterioration, clinical progression, or who have commenced subsequent anticancer therapy will be followed for PK and survival. Efficacy assessments are to be done according to [Table 3](#) (ie, until radiological progression plus an additional regularly scheduled follow-up scan or death; whichever comes first).

Survival

All patients in the study will be followed up for survival.

Data Review Committee:

A DRC will be established prior to the initiation of the study and will review the safety and PK data. The DRC membership will comprise of participating Investigators and representatives from both AstraZeneca (Pharmacovigilance Scientists for durvalumab and tremelimumab, PK Scientist, Study Physician and Biostatistician) and IQVIA (Study Physician, Safety Physician and Biostatistician). On a case-by-case basis, the DRC may also seek advice from pediatric oncologists with the required site specialization expertise.

Recommendations and decisions will be made through consensus of opinion amongst the DRC members with all decisions being documented and distributed to DRC members.

The key tasks of the DRC members will be to review the data recorded in the clinical database in conjunction with the PK data to:

1. Determine whether DLTs have occurred
2. Decide whether additional patients should be added to a cohort
3. Recommend de-escalating a dose that was poorly tolerated or escalating a dose if PK exposures inferior to those observed in adults, were achieved
4. Declare that dose finding is complete
5. Recommend a Phase II dose to be explored in the dose-expansion phase of the study
6. Perform a benefit/risk assessment at the completion of safety data analysis for children <1 year old prior to enrolling a patient less than 1 year old; notify local health authority of decision, if applicable, as per local requirements
7. Put enrollment on hold
8. End the study.

During the dose-expansion phase, the DRC will review safety, tolerability, PK, and efficacy data to make consensual decisions on cohort expansion or closure, and end the study, among others.

Statistical methods

There is no formal statistical testing for the dose-finding phase of the study.

The dose-expansion phase of the study will formally test the following hypothesis:

- H0: ORR \leq 10%
- H1: ORR >10%.

The test will be performed for the SARCOMA cohort and it will be done at the 1-sided 5% level. No formal statistical testing will be performed for the STO cohort.

Five analysis sets will be used for data analysis:

- The full analysis set (FAS) will include all patients who were assigned to treatment and received at least 1 dose of study treatment. The FAS (or subset of the FAS specified below) will be used for all efficacy analyses. Patients will be summarized and analyzed according to their assigned study treatment, regardless of the treatment actually received.
